4.2 Secondary Subjects

Not applicable

4.3 Number of Subjects

A. Total Number of Subjects

Aim 1: Participants for the design sessions will be 10-15 adults in total and 10-15 youth in total. Each design session will be a focus group of approximately 5-8 people or one-on-one interview and we anticipate 2 design sessions for each group (adults and youth). One adult session will be in Spanish to be inclusive of participants with limited English proficiency.

Aim 1a: 15 participants

Aim 2: 100 participant dyads (1 youth + 1 adult = 1 dyad), 200 total

Aim 3: 10 adults and 10 youth will be recruited for phone interviews. In the first cohort, all members of the intervention group and in the school cohort all participants will complete questionnaires. () .

B. Total Number of Subjects If Multicenter Study

Not applicable

C. Feasibility

In the US, 33% of individuals have HTN⁶ and for adults with HTN, BP control decreased from 54% in 2013-2014 to 44% in 2017-2018.⁷ BP is elevated at almost half (44%) of all ED visits- compared to 27% of primary care doctor visits.⁸ Data demonstrates that ED patients' elevated BP is from HTN, and not a result of pain or anxiety from the ED visit.^{9,10} From 2006 to 2012, HTN-related ED visits made up 24% of all ED visits, and rose 5% per year.¹¹

Based on the high prevalence of uncontrolled HTN in the US, and especially in ED patients compared to patients in other settings, we anticipate that it will be feasible to recruit our study sample size of 100 patients for Aim 2 given we are recruiting from a large ED of 70,000 patients. (Aim 1 sample size of 20-30 participants is also feasible given the prevalence of HTN in the community.)

For the school cohort, there are about 200 students at the school, so we anticipate that recruiting enough students for the study will be feasible, especially because all study procedures will take place at school or at home.

4.4 Consent Procedures

A. Consent Process

▪ **Location of Consent Process**

Aim 1: Participants will receive an information letter about the study, and their consent to participate will be their participation in the discussion. Parental permission will take place electronically through RedCap for participants 15-17 years old, and will be required in order for 15-17 year olds to participate.

Aim 1a: Participants will receive an information letter about the study, and their consent to participate will be their participation in the discussion. Parental permission will take place electronically through RedCap for participants 15-17 years old, and will be required in order for 15-17 year olds to participate.

Aim 2: For first cohort: Adult consent by the ED patient will take place in the ED through RedCap so that the study team can collect their baseline BP and other characteristics at baseline. Assent and parental permission for youth participants will take place electronically through RedCap. A member of the study team will walk the youth participant and their parent/legal guardian through the study and appropriate form via phone or Zoom.

School cohort: Adult and youth consents and parental permission forms will be completed electronically through Redcap. A member of the study team will describe the study, answer questions about the study, and will consent the participant in person or on Zoom while the participant signs the form on Redcap.

Aim 3: Interview: Participants will receive an information letter about the study, and their consent to participate will be their beginning the interview. Parental permission will take place electronically through RedCap for participants 14-17 years old, and will be required in order for 14-17 year olds to participate.

For the school cohort: The interview will be included in the consent form for the rest of the study.

- **Ongoing Consent**

Not applicable

- **Individual Roles for Researchers Involved in Consent**

Participants will be consented by the PI ([name]) and research assistants. (

- **Consent Discussion Duration**

It is expected that the consent/assent/parental permission process (for each Aims) will take approximately 5 minutes each.

- **Coercion or Undue Influence**

For first cohort: In order to minimize the possibility of coercion or undue influence on potential subjects, subjects in Aim 2 will only be approached for study consent after they have completed their evaluation in the emergency department and their care team has approved of them being approached by the study team. Subjects in all Aims will also be informed that participation is voluntary and will not affect their relationship with the university/hospital if they decline to participate.

For school cohort: It will be stressed to potential subjects that participation in the study is voluntary.

- **Subject Understanding**

Participants will be given ample opportunity to ask any questions they may have about the study, and a trained member of the study team will answer their questions.

B. Waiver or Alteration of Consent Process

Not applicable

C. Documentation of Consent

- **Documenting Consent**

For the first cohort, Aim 2 adult participants will be consented for the study in person in the ED, at which time they will complete an electronic consent in RedCap or sign a paper consent document. All other participants (parents/legal guardians in Aims 1, 1a, and 3, and youth and parents/legal guardians in Aim 2, adults in the school cohort) will sign their consent/assent/parental permission document electronically in RedCap.

- **Waiver of Documentation Of Consent (i.e., will not obtain subject's signature)**

For Aims 1, 1a, and 3 (first cohort), participants will receive an information letter about the study, and their consent to participate will be their participation in the discussion. For the school cohort, the interview will be included in the study consent form.

4.5 Special Consent/Populations

A. Minors-Subjects Who Are Not Yet Adults

- **Parental Permission**

Parental permission will be obtained for study participants who are less than 18 years old for all Aims.

- **Non-Parental Permission**

Legal guardians can provide parental permission. Proof of legal guardianship will be shown to the study team, and it is expected that this will not be a problem to exhibit because they need this proof for school.

▪ **Assent Process**

No assent forms will be used in this study.

Participants who are 14-17 years old will follow the same consent process as adults for Aims 1, 1a, and 3. Participants who are 14-17 years old will follow the same consent process as 18 year olds in the “Youth” group. (Each cohort for Aim 2 will have 2 consent forms- one for the adults, and one for youth pair in their dyad.)

▪ **Documentation of Assent**

Not applicable

Aim 2 youth will sign a consent form electronically in RedCap. A member of the study team will walk the participant through the study and appropriate form via phone or Zoom.

▪ **Reaching Age of Majority During Study**

Not applicable

B. Wards of the State

Not applicable

▪ **Research Outside of NJ Involving Minors**

Not applicable

C. Non-English-Speaking Subjects

In addition to English, participants who are Spanish-speaking will also be eligible for the study.

▪ **Process for Non-English-Speaking Subjects**

Research assistants [name], and [name] have translated all patient-facing documents (consent, recruitment script, etc) into Spanish. Research assistants (RA) [name] and [name], and [name] are fluent Spanish-speakers and will interact with Spanish-speaking patients for research tasks such as consenting and focus groups and interviews for Aims 1, 1a, and 3.

▪ **Short Form Consent for Non-English Speakers**

The English consent form is translated into Spanish for Non-English Speakers.

D. Adults Unable to Consent / Decisionally Impaired Adults

Not applicable

4.6 Economic Burden and/or Compensation for Subjects

A. Expenses

Participants will incur no expenses for study participation.

B. Compensation/Incentives

Aim 1: Participants will receive a \$20 gift card.

Aim 1a: Participants will receive a \$10 gift card.

Aim 2: In the first cohort, youth in both arms will receive a \$20 gift card after completing baseline assessments, a \$20 gift card after completing the first 3 weekly modules (halfway

through the intervention), a \$20 gift card after completing all 6 weekly modules (end of intervention) and questionnaires one week later, and a \$10 gift card after completing questionnaires two months after the end of the intervention.

Adults in both arms will receive a \$20 gift card after completing baseline assessments and a \$40 gift card at each follow-up visit for BP check (1 week and 2-months). Adults will also receive transportation vouchers (for either parking or public transit) for follow-up visits.

In the school cohort, adults and youth will receive \$80 in gift cards total if they complete the study. Youth will receive: a \$20 gift card after completing the second in-school session, a \$20 gift card after completing the first 3 weekly modules (halfway through the intervention), a \$20 gift card after completing all 6 weekly modules (end of intervention) and questionnaires, and a \$20 gift card after completing questionnaires 1 month after the end of the intervention. Adults will receive: a \$20 gift card after completing the second in-school session, a \$20 gift card after completing the first 3 weekly modules (halfway through the intervention), a \$20 gift card after completing all 6 weekly modules (end of intervention) and questionnaires, and a \$20 gift card after completing questionnaires 1 month after the end of the intervention. **Aim 3:** Interview participants will receive a \$10 gift card per interview for their time.

C. Compensation Documentation

To document compensation, we will keep a master list of date, subject name, amount and type of compensation received.

4.7 Risks of Harm/Potential for Benefits to Subjects

A. Description of Risks of Harm to Subjects

▪ Reasonably Foreseeable Risks of Harm

This is a minimal risk study. The only foreseeable risk of harm is a possible loss of confidentiality, however procedures will be in place to minimize risks of harm.

▪ Risk of Harm from an Intervention on a Subject with an Existing Condition

Not applicable

▪ Other Foreseeable Risks of Harm

None

▪ Observation and Sensitive Information

Not applicable

B. Procedures which Risk Harm to Embryo, Fetus, and/or Pregnant Subjects

Not applicable

C. Risks of Harm to Non-Subjects

Not applicable

D. Assessment of Social Behavior Considerations

Not applicable

E. Minimizing Risks of Harm

The PI is responsible for protecting the confidentiality of subjects' data. All data will be entered into electronic database (RedCap). RedCap is a secure, web-based application. There will be no paper charts/data entry. This will minimize the potential for loss of information and breach of privacy.

Patient confidentiality will be maintained through secured, password protection computerized data collection. All documents and information about this study will be kept confidential in accordance

with federal, state, and local laws and regulations. The results of this study will be published. If results are published, no subject will be identified by name.

- **Certificate of Confidentiality**

Not applicable

- **Provisions to Protect the Privacy Interests of Subjects**

Patient confidentiality will be maintained through secured, password protection computerized data collection. All documents and information about this study will be kept confidential in accordance with federal, state, and local laws and regulations. The results of this study will be published. If results are published, no subject will be identified by name.

F. Potential Benefits to Subjects

It is possible that adult participants with uncontrolled hypertension in the intervention arm of the randomized controlled trial (RCT) (Aim 2 first cohort) may experience a decrease in their blood pressure. We have also hypothesized that youth in both arms of the RCT (Aim 2 first cohort) may experience increased knowledge and self-empowerment. First the school cohort, participants may show an increase in hypertension knowledge, confidence in HTN management, and/or health behavior changes.

5.0 Special Considerations

5.1 Health Insurance Portability and Accountability Act (HIPAA)

HIPAA authorization language will be included in the consent for Aim 2 first cohort, as we will collect information from the patient's medical record.

5.2 Family Educational Rights and Privacy Act (FERPA)

Not applicable

5.3 Code of Federal Regulations Title 45 Part 46 (Vulnerable Populations)

A. Special Populations

- Children

5.4 General Data Protection Regulation (GDPR)

Not applicable

5.5 NJ Access to Medical Research Act (Surrogate Consent)

Not applicable

6.0 Data Management Plan

6.1 Data Analysis

Aim 1: *Quantitative*: Questionnaire data will be analyzed descriptively. *Qualitative*: Audio recordings will be transcribed verbatim, and will be analyzed using Gale's Framework Method.⁴² As such, three members of the study team will conduct open coding for all transcripts and will meet to agree on a working analytical framework. Categories will be grouped into subsequent themes as related to the digital badge. The PI will then refine the digital badge based on findings from the design sessions with input from mentors.

Aim 1a: Qualitative data will be collected from youth on their feedback on the hypertension knowledge assessment tool. In addition, we will analyze item discrimination and internal reliability of the tool based on their completion of the tool in its entirety. Data from a brief demographic survey will be analyzed descriptively.

Aim 2: Descriptive statistics will be used to assess participant characteristics and covariate balance across study arms. To determine balancing of important measures that may influence outcome variables, the analysis will implement t-tests for continuous variables and chi-square tests for categorical variables. STATA will be used to carry out all statistical analysis. Analysis will include mean BP change from baseline to 2-month follow-up for each arm using a t-test. Multivariate linear regression analysis will also be used to compare the two groups, including a dummy variable for group, baseline BP, and any covariates found to be unbalanced across arms. For youth empowerment, pre- and post-intervention data will be compared with significance testing via t-test.

Aim 3: *Quantitative:* Quantitative data will be analyzed descriptively. *Qualitative:* Interviews will be analyzed using Gale's Framework Method⁴² (see Aim 1 for more details).

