Due to challenges recruiting youth through adults in the ED, we will be adding a cohort to the study. For this new cohort of the study, we will recruit interested youth from New Brunswick Health Sciences Technology High School (NBHSTHS). Students will be asked to pair themselves with an adult (18+) (preference for adult who has been diagnosed with hypertension, but not mandatory) with an existing relationship with the student where it would be feasible to complete an online module together 1 hour per week for 6 weeks. The adult must be fluent in English or Spanish and the student must be able to speak the fluent language of the adult. We will evaluate the youth-led digital hypertension (HTN) education intervention- an electronic tool to guide youth through learning and then teaching and supporting adults on how to control hypertension (for adults with hypertension) and how to avoid it (for adults without hypertension). Outcomes of interest are HTN knowledge, confidence in HTN management, and health behavior changes in participants, which will be obtained through pre- and post- intervention assessments. We will also be exploring outcomes of participant acceptability, feasibility, and fidelity of the intervention.

A. Objectives

Specific aims are:

Aim 1: Create a youth-led HTN education digital badge by means of user-centered design methods and community engagement with adults with HTN and youth to obtain input on the contents of the digital badge prior to implementation.

Aim 1a: The hypertension knowledge assessment being used in the study has not been used before on youth or Spanish-speaking populations, so we will obtain feedback on the assessment from these groups.

Aim 2: Evaluate the effectiveness of a youth-led HTN education digital badge intervention on the primary outcome of mean systolic BP (SBP) and diastolic BP (DBP) change in adults with uncontrolled HTN at 2-months post-intervention compared to the control group. Additionally, evaluate change in HTN knowledge and youth self-efficacy. Additionally, we will measure confidence in HTN management, and health behavior changes in participants.

Aim 3: Evaluate the implementation process of the youth-led HTN education digital badge by collecting qualitative and quantitative data on acceptability, feasibility, and fidelity of the intervention by participants.

B. Hypotheses / Research Question(s)

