Arm 1- Intervention: Participants in the intervention arm will receive the youth-led HTN education digital badge to complete, which will be comprised of a 6-week playlist of one module per week comprising the playlist. Youth will learn from the module and will teach the adult in their dyad about hypertension education in each week's themed module.

Arm 2- Control: For dyads that are randomized into the control arm, the youth will complete job readiness digital badges. These will include a Career & Job Readiness digital badge playlist, with such playlists as, "Interview Preparation", "Resume Ready", and "Professionalism". While this group may complete multiple digital badges, the total time needed to complete the badges will be approximately equivalent to that of the intervention group (eg. one hour per week for each arm).
9. For both arms, youth must submit evidence of completion (eg. photograph, document) as specified in the playlist's instructions. Evidence will be reviewed by the study team and a digital badge is received if all XPs are satisfactorily completed. If not satisfactorily completed, then a note will be sent back to the youth on how to fix or improve the evidence and resubmit.

10. Adult participants in both arms return to RWJUH for follow-up BP check and complete follow-up assessments- blood pressure self-care scale, hypertension knowledge assessment, and self-efficacy to manage hypertension scale. They will receive an incentive for returning at 1 week and 2 months after completion of digital badge. Youth will complete follow-up assessments of hypertension knowledge and confidence in managing blood pressure of adults at the same timepoints but will be done remotely/electronically.

Due to challenges recruiting youth through adults in the ED, we will be adding a cohort to the study. For this new cohort of the study, we will recruit interested youth from NBHSTHS. Students will be asked to pair themselves with an adult (18+) (preference for adult who has been diagnosed with hypertension) with an existing relationship with the student where it would be feasible to complete an online module together 1 hour per week for 6 weeks. The adult must be fluent in English or Spanish and the student must be able to speak the fluent language of the adult. For this cohort, study procedures are as follows:

1. We will recruit students at NBHSTHS for information sessions (see youth recruitment flyer).

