Questionnaire: At the conclusion of each hypertension education module in the intervention, all participants in the intervention group will be asked to complete a questionnaire on the intervention's acceptability and feasibility as part of the requirement for module completion. Participants must complete the questionnaires to receive their study incentive.

Interviews: We will also conduct one-on-one phone interviews with interested participants from the intervention group for more in-depth information on intervention acceptability, feasibility, and fidelity. These will take place halfway through the intervention and at the end of the intervention. Interviews will be available in English and Spanish, and be audio recorded.

B. Data Points

Aim 1 (Group 1): Participation will be a one-time design session that will take place prior to the start of the RCT.

Aim 1a: Participation will be a one-time cognitive interview session.

Aim 2 (Group 2): For the first cohort, BP will be collected at baseline in the ED and at 1 week and 2-month post-intervention follow-ups at RWJUH. Pre- and post-intervention change in HTN knowledge, adult BP self-care, adult self-efficacy to manage HTN and youth confidence in managing adult BP will be collected during the same timepoints.

For the school cohort, youth and adult participants will complete study assessments after consent is signed. Fidelity of the intervention will be collected on youth the following week, and youth will complete a HTN knowledge assessment at the end of this session. At the end of each of the 6 intervention modules, participants will complete module feedback assessments. At the end of the 6 week intervention and then 1 month after the end of the 6 week intervention, all participants will complete study assessments.

Aim 3 (Group 2): Implementation data points will be collected at the end of each module (surveys) and at the midpoint and end of the intervention period (6 weeks post-baseline) (interviews).

C. Study Duration

Aim 1 (Group 1): Participation will be a one-time design session that will last approximately 1.5 hours.

The duration of this aim is expected to be about 3 months.

Aim 1a: Participation will be a one-time cognitive interview session that will last approximately 30 minutes. The duration of this aim is expected to be about 3 months.

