1.6 Study Variables

A. Independent Variables, Interventions, or Predictor Variables

Aim 1: Not applicable

Aim 1a: Not applicable

Aim 2: For the first cohort, outcomes will be compared for dyads randomized to the intervention arm versus those randomized to the control arm, where youth participants in the intervention arm will complete the youth-led HTN education digital badge with their hypertensive adult and youth participants in the control arm will complete job readiness digital badge(s).

For the school cohort, we will be looking at changes before and after the 6-week intervention in adult and youth participants.

Aim 3: Not applicable

B. Dependent Variables or Outcome Measures

Aim 1: Not applicable

Aim 1a: Not applicable

Aim 2: For the first cohort, the primary outcome is change in BP (in mm Hg) from baseline to 1 week and 2 months later. We will also collect secondary outcomes of pre- and post-intervention change in HTN knowledge, adult BP self-care, adult self-efficacy to manage HTN and youth confidence in managing adult BP during the same timepoints.

For the school cohort, outcomes of interest are HTN knowledge, confidence in HTN management, and health behavior changes in participants. (Same outcomes as the first cohort except for the BP change.)

Aim 3: Not applicable

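### No stated BP analysis uses the 1-week reading, so an adult seen at 1 week but not at 2 months adds nothing to the 2-month arm comparison

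*Combined protocol and SAP*

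**What the plan says.** For the ED cohort, section 1.3 B sets three BP readings: "BP will be collected at baseline in the ED and at 1 week and 2-month post-intervention follow-ups at RWJUH". Section 1.3 A, step 10, applies this to everyone randomised: "Adult participants in both arms return to RWJUH for follow-up BP check". The two follow-up visits are separate occasions. Section 4.6 B pays adults in both arms a "gift card at each follow-up visit for BP check (1 week and 2-months"), so an adult can attend one and miss the other.

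The primary outcome is described in two ways. Aim 2 in section 1.1 sets it as BP "change in adults with uncontrolled HTN at 2-months post-intervention compared to the control group". Section 1.6 B says "the primary outcome is change in BP (in mm Hg) from baseline to 1 week and 2 months later".

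Section 6.1 holds the only BP analyses. The first is "Analysis will include mean BP change from baseline to 2-month follow-up for each arm using a t-test". The second is "Multivariate linear regression analysis will also be used to compare the two groups, including a dummy variable for group, baseline BP, and any covariates" that prove unbalanced between arms. The second sentence does not say which follow-up BP is the outcome. Neither sentence mentions the 1-week BP, a visit term or a subject effect. The document gives no missing-data method and defines no analysis population.

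**The concern.** A change score or a single-outcome regression needs the 2-month value. With no missing-data method, an adult who has a 1-week but no 2-month reading falls out of the 2-month comparison. The 1-week change that section 1.6 B names as primary has no stated analysis at all.

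Loss between the two visits is plausible. Section 1.1 describes the adults as hard to reach, and the outcome requires coming back to the hospital. If the adults who fail to return at 2 months are selected by their 1-week BP, and the selection differs by arm, a regression on group and baseline BP alone is biased. The reading that could correct this has already been collected and is left unused. The arms do differ in one respect that might affect return: intervention adults are taught weekly and control adults are not.

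**Working it through.** The plan has no figure to reproduce. Section 1.5 defers the sample size calculation, and no SD, correlation or dropout rate is stated.

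**Inputs**
- From the document: "100 participant dyads (1 youth + 1 adult = 1 dyad), 200 total" for Aim 2 (section 4.3 A).
- Assumed: all 100 dyads are in the RCT at 1:1, so 100 / 2 = 50 adults per arm.
- Assumed: SD 16 mmHg; correlation of baseline with each follow-up 0.4; correlation ρ of 1-week with 2-month BP 0.5 to 0.65.
- Assumed loss: 10% before the 1-week visit, then 25% of the rest. Missing at 2 months = 1 − 0.90 × 0.75 = 0.325, about 32%. The alternative split, 25% then 10%, gives the same total.

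**Precision under random loss**

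Let n1 be the adults per arm with a 1-week reading and nc those who also have a 2-month reading. Let r be the 1-week/2-month correlation given baseline. For monotone missing data, the variance of the likelihood estimate relative to complete-case regression is (1 − r²) + r² × (nc/n1).

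- r = (ρ − 0.4²) / (1 − 0.4²). For ρ = 0.5, r = 0.34/0.84 = 0.405. For ρ = 0.65, r = 0.49/0.84 = 0.583.
- Loss 10% then 25%: nc/n1 = 0.75. The variance ratios are 1 − 0.164 × 0.25 = 0.959 and 1 − 0.340 × 0.25 = 0.915, so the SE is 2.1% and 4.3% smaller. Simulation agrees: 3.63 to 3.55 (2.2%) and 3.56 to 3.41 (4.2%).
- Loss 25% then 10%: nc/n1 = 0.90. The ratios are 0.984 and 0.966, so the SE is 0.8% and 1.7% smaller. Simulation gave 3.71 to 3.69 (0.5%) and 3.64 to 3.59 (1.4%).
- Wider check, with 50 per arm seen at 1 week, 20% of them missing 2 months and r from 0.3 to 0.7: the SE is 0.9% to 5.0% smaller, and 40 complete cases per arm become an effective 40.7 to 44.3.

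**Bias in the 2-month contrast**

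Simulated trials (3,000 or 4,000 per scenario where the count is recorded) compared complete-case regression at 2 months with the likelihood estimate. The latter models 1-week BP given baseline and arm, then 2-month BP given baseline, 1-week BP and arm. Figures are absolute bias in mmHg.

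| How loss after 1 week depends on 1-week BP | Complete case, 10% then 25% lost | Complete case, 25% then 10% lost | Using 1-week BP |
|---|---|---|---|
| Not at all (random) | about 0.1 or less | about 0.1 or less | about 0.1 or less |
| Equally in both arms, no true effect | about 0.1 or less | about 0.1 or less | about 0.1 or less |
| In one arm only | 0.6 to 2.0 | 0.5 to 0.6 | about 0.1 or less |
| In opposite directions by arm | 1.3 to 4.2 | 1.0 to 1.5 | about 0.1 or less |

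The third column and the middle of the second use a logistic slope of 1 per SD of 1-week BP. At that slope the second column is 1.1 to 1.8 for one arm and 2.4 to 3.5 for opposite directions; its outer limits come from repeat runs at the same arm size and SD. In one of those sets the likelihood estimate was within 0.15 rather than 0.1.

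A separate run with SD 18, about 20% missing, and loss more likely for intervention adults with a high 1-week BP gave −1.21 for complete cases against −0.02, when the true effect was 0. With a true effect of −5 it gave −5.92 against −4.92. In that direction the bias favours the intervention.

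**The case against.** Several counterpoints stand.

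- Only the t-test sentence names 2 months. That the regression is also at 2 months is inferred from the preceding sentence and Aim 2. Since section 1.6 B includes 1 week, the regression could be meant for that visit too.
- A reader might infer that the planned analysis is biased as it stands. The documents do not support that. Bias needs loss that depends on 1-week BP differently by arm; random loss, or the same dependence in both arms with no true effect, gives essentially none. Nothing in the protocol suggests dependence in opposite directions.
- A reader might also infer that control adults have nothing to do in the study and will drop out more. In fact they have the same BP visits and assessments (section 1.3 A, step 10) and the same gift cards and transport vouchers (section 4.6 B). Only the weekly teaching differs.
- That difference acts mostly before the 1-week visit. The first interval covers youth enrolment, the 6-week badge and one more week, so it may well carry most of the loss. The lower ends of the ranges then apply.
- This is a pilot with no power claim, and ED recruitment has been difficult. With 25 adults per arm the SE is about 5.1 to 5.2 mmHg, so a bias of 1 to 2 mmHg is well below one SE.

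These points limit the size and certainty of the problem. They do not remove it: Hypothesis 2a still compares BP between arms, and a small trial has little reason to leave collected readings out of its analysis.

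**Conclusion.** The concern holds as a gap in the analysis plan, not as a demonstrated error. No stated BP analysis uses the 1-week reading, no missing-data method is given, and the 1-week change named in section 1.6 B has no analysis. Under the assumed inputs, complete-case bias runs from about 0.1 mmHg or less in the ordinary cases to about 0.5-2 mmHg with one-arm dependence and about 1-4 mmHg with opposite dependence. The case for change rests on protection against arm-specific loss and on giving the 1-week outcome an analysis, more than on the SE gain of about 1-5%. The size depends on the loss pattern, the correlations and 50 adults per arm, none of which the protocol states.

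**What to change.** In section 6.1, for SBP and DBP separately, replace the t-test and regression as the main arm comparison with one mixed model for repeated measures:

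- Include every randomised adult with at least one follow-up BP.
- Fit arm, visit, arm-by-visit, baseline BP and baseline-by-visit, with an unstructured covariance across the two follow-up visits. The baseline-by-visit term matches the estimator checked above.
- Take the 2-month arm contrast as the primary estimate and the 1-week contrast from the same model.
- Keep the planned regression, stated explicitly as 2-month, as a sensitivity analysis.
- Say whether covariates found unbalanced enter the mixed model.
- Reconcile Aim 2 with section 1.6 B, so that the primary time point is defined once.

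The cost is a few lines of text. The planned software fits the model, and no new data or visits are needed. The limits should be stated: the model assumes loss is explained by observed BP, and it adds essentially nothing for adults who miss both visits.
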